### **5.5.4 Effect of MEDI-563 on Asthma Control**

The ACQ is a 6-item subject reported questionnaire to assess the recall over the prior week with 6 items addressing night-time waking, symptoms on waking, activity limitation, shortness of breath, wheeze, and rescue short-acting beta agonist use. Questions are rated on a 7-point Likert scale from 0 (no impairment) to 6 (maximum impairment). Final scores are the mean of the 6 items and results in a score between 0, well controlled to 6, extremely poor controlled (Juniper 1999). Mean, mean change from baseline, and responder frequency tables will be provided. Individual subjects with score changes of -0.5 or less will be considered

responders. A change of -0.5 is considered to be a minimally important difference on the ACQ.

### **5.5.5 Effect of MEDI-563 on Variability of Airflow Obstruction**

The analysis of the effect of MEDI-563 on variability of airflow obstruction (FEV1 at the site and FEV1 and PEF at home) through Study Day 84 will be primarily descriptive. Mean and mean change from baseline will be provided for office spirometry (FEV1). Two-sample t-tests may be used to explore changes from baselines in subject FEV1 between the combined MEDI-563 treatment groups and the placebo group.

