- 14) The investigator has determined that the subject is clinically stable and the  $FEV_1 \geq 30\%$  predicted prior to receiving investigational product on Study Day 0,

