## **5 Statistical Considerations**

### **5.1 General Considerations**

All data will be provided in data listings sorted by treatment groups (MEDI-563 0.3 mg/kg, MEDI-563 1.0 mg/kg, or placebo), and visit number. Summary data will be presented in tabular format by treatment groups. Categorical data will be summarized by the number and percentage of subjects in each category. Continuous variables will be summarized by descriptive statistics including N, mean, standard deviation, median, and range. Statistical hypothesis testing, if appropriate, will be performed for the primary endpoint with a 2-sided test.

A comprehensive statistical analysis plan will be developed and approved prior to the database lock.

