### **5.2 Sample Size and Power Calculations**

#### **5.2.1 Planned Sample Size**

Sample size calculations have been performed for the primary endpoint of proportion of subjects with asthma exacerbations at Week 12 to allow for hypothesis testing. Sample size calculations are based on Fisher's exact test with  $\alpha = 0.05$  (2-sided) for testing the difference between the combined MED-563 treatment groups ( $n=72$ , 0.3 mg/kg and 1.0 mg/kg) and the combined placebo group ( $n=36$ ). Assumptions include: (1) The proportion of placebo subjects with asthma exacerbations at Week 12 is 60% and (2) There will be  $\geq 50\%$

reduction in the proportion of subjects with asthma exacerbations at Week 12 in the combined MEDI-563 (0.3 and 1.0 mg/kg) treatment groups. The sample size may be re-estimated using the proportion of subjects with asthma exacerbations (relapsed or de novo) up to the first interim analysis to preserve the power around 80% if the proportion of subjects with asthma exacerbations is different from the assumptions listed above.

There will be no adjustment on Type 1 error rate for sample size re-estimation in this study. However, the true overall type I error rate will be greater than 0.05 if the multiplicity adjustment is taken into account in the calculation. With 108 evaluable subjects, the statistical power to detect statistically significant differences in the proportion of subjects with asthma exacerbations at Week 12 in the combined MEDI-563 treatment groups and the placebo group will be 80% based on the above assumptions. Power calculations were performed using nQuery Advisor software program Version 6.01.

Table 5.2.1-1 and [Table 5.2.1-2](#) present the probability of observing at least one infrequently occurring event when assuming a range of potential observed event rates and exact binomial 95% confidence intervals to assess the precision of estimates of the event rate for each individual treatment group (n=36) and combined MEDI-563 treatment group (n=72).

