### 5.4 Primary Endpoint

The primary objective of this study is to evaluate the effect of two IV dose regimens of MEDI-563 (0.3 and 1.0 mg/kg) on the proportion of subjects with asthma exacerbations (relapsed or de novo) at Week 12 in adult subjects who required an urgent healthcare visit for treatment of an acute asthma exacerbation. The formula that will be used to evaluate the proportion of subjects with asthma exacerbations in the combined MEDI-563 treatment groups at Week 12 will be as follows:

- $$\frac{\text{(Number of subjects with at least one asthma exacerbation in the combined MEDI-563 treatment groups [0.3 and 1.0 mg/kg] at Week 12)}}{\text{(Number of total evaluable subjects in the combined MEDI-563 treatment groups [0.3 and 1.0 mg/kg] at Week 12)}}$$

The Fisher’s exact test will be performed for testing the differences in proportion of subjects with asthma exacerbations at Week 12 between the combined MEDI-563 treatment groups and the placebo group at an alpha level of 0.05.

The number of asthma exacerbations at Week 12 for each MEDI-563 treatment group (0.3 and 1.0 mg/kg) versus placebo will also be reported. The Fisher’s exact test may be performed for testing this endpoint.

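### The only between-arm comparison named for office FEV1 is an unadjusted t-test on change from baseline; ANCOVA with Day 0 FEV1 and the eosinophil stratum would be more precise at no cost

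*Protocol*

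**What the plan says.** Section 5.5.5 says that the analysis of airflow obstruction "through Study Day 84 will be primarily descriptive". For office FEV1 it plans the mean and the mean change from baseline, and then adds: "Two-sample t-tests may be used to explore changes from baselines in subject" FEV1, combined MEDI-563 against placebo. The Study Abstract (Assessment of Endpoints) repeats this. Neither place names a covariate or another between-arm method for FEV1.

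Elsewhere the protocol provides what an adjusted analysis would need:

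- **Baseline FEV1.** The Study Day 0 visit in Section 3.5 lists spirometry among the assessments to be finished before dosing. The protocol does not say outright that Day 0 is the FEV1 baseline. It is the natural reading, because screening accepts either spirometry or peak flow.
- **Stratum.** Section 2.3 stratifies randomization by blood eosinophils, above 450 against 450 or fewer per mm3.
- **Arm sizes.** Section 3.4.2 plans 72 evaluable subjects on MEDI-563 and 36 on placebo.
- **Timing of baseline.** Dosing is within 7 days of meeting eligibility (Section 3.4.2), after an urgent visit for an acute attack. Inclusion criterion 14 requires, before dosing: "The investigator has determined that the subject is clinically stable and the" FEV1 is at least 30% predicted.

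Formal testing is placed elsewhere. Section 5.1 says that hypothesis testing, if appropriate, will be "performed for the primary endpoint with a 2-sided test".

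**The concern.** A change score subtracts the whole baseline value, which amounts to assuming that follow-up FEV1 rises by one unit for each unit of baseline FEV1. That assumption is doubtful here. Day 0 falls between the day of screening and about a week later, in people who have just had an exacerbation, and follow-up is measured as late as Day 84. A baseline taken during recovery may predict later FEV1 only moderately, so the true slope could be well below 1.

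Two things follow if it is. Part of the baseline noise is carried into the outcome, which widens the confidence interval for the treatment difference. And a chance difference in mean baseline between the arms is over-corrected, because the subtraction removes more than the slope warrants. With 36 placebo subjects, a chance difference of some size is to be expected.

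FEV1 is also the only continuous efficacy outcome for which the protocol names a between-arm test. If the comparison is made at all, it should use the better estimator that the scheduled data allow.

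**Working it through.** **The plan's own figure.** The protocol states power only for the primary endpoint: power for the combined MEDI-563 "treatment groups and the placebo group will be 80% based on the above assumptions". The inputs are Fisher's exact test, two-sided alpha 0.05, placebo 60%, a 50% reduction giving 30%, and 36 against 72 subjects. Exact enumeration gives 81.1%, so the stated 80% reproduces. It does not depend on how FEV1 is analysed. No SD, correlation or power is given for FEV1.

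**Variance of the two estimators.** Let rho be the correlation between baseline and follow-up FEV1, and k the baseline SD divided by the follow-up SD. Both are assumptions. In units of the follow-up variance, for large samples:

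- change score: 1 + k² − 2·rho·k
- ANCOVA on baseline: 1 − rho²
- difference: (1 + k² − 2·rho·k) − (1 − rho²) = (k − rho)²

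The difference is never negative. It is zero only when rho = k, that is, when the true slope rho/k equals 1.

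With equal SDs (k = 1) the ratio is 2(1 − rho)/(1 − rho²) = 2/(1 + rho). The last column is the power of ANCOVA for an effect that the change-score t-test would detect with 80% power at 36 against 72:

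| rho | Change score | ANCOVA | Ratio | ANCOVA power |
|---|---|---|---|---|
| 0.3 | 1.40 | 0.91 | 1.54 | 93.5% |
| 0.5 | 1.00 | 0.75 | 1.33 | 89.9% |
| 0.7 | 0.60 | 0.51 | 1.18 | 86.0% |
| 0.9 | 0.20 | 0.19 | 1.05 | 82.0% |

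**Unequal SDs.** The ratio depends strongly on k:

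| rho | k = 0.8 | k = 1 | k = 1.25 |
|---|---|---|---|
| 0.5 | 0.84/0.75 = 1.12 | 1.33 | 1.3125/0.75 = 1.75 |
| 0.7 | 0.52/0.51 = 1.02 | 1.18 | 0.8125/0.51 = 1.59 |
| 0.8 | 0.36/0.36 = 1.00 | 1.11 | 0.5625/0.36 = 1.56 |

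The cell with ratio 1.00 is the case where the true slope is 1 (0.8/0.8).

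**Chance imbalance.** The standard error of the difference in baseline means is sqrt(1/72 + 1/36) = 0.20 baseline SDs. Given an observed imbalance, the change-score and ANCOVA estimates differ by (1 − slope) times that imbalance. With equal SDs the slope is rho. A one-standard-error imbalance then separates the two by 0.7 × 0.20 = 0.14 SD at rho 0.3, 0.5 × 0.20 = 0.10 SD at rho 0.5, and 0.1 × 0.20 = 0.02 SD at rho 0.9.

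**Eosinophil stratum.** The gain from adding it cannot be computed from the protocol, which does not relate eosinophil level to FEV1 numerically.

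**The case against.** The strongest reply is that the protocol hardly commits itself. The t-test is only permitted, the analysis is mainly descriptive, and Section 5.1 defers to a full analysis plan in which an ANCOVA could still be specified. No sample size, alpha or decision rule depends on FEV1. All of that stands, and it keeps the point small. It does not remove it: the protocol is not silent here but names a method, and that method is the weaker of two that need the same data.

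A reader might also infer more than the documents support:

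- **That baseline is ignored.** It is not. A change score uses it by subtraction; what is missing is its use as a covariate with an estimated slope.
- **That the test is biased or invalid.** Under randomization it is unbiased and keeps its type I error. Leaving out the stratum is, if anything, conservative. The imbalance figures above are conditional on the baseline that happens to be observed.
- **That Day 0 FEV1 is at most 70% predicted.** That ceiling (inclusion criterion 8, FEV1 or PEF) applies after 1 hour of treatment at the urgent visit. Day 0 may be days later and requires clinical stability. The 30% figure is a floor for eligibility, not an expected value.
- **That a change score is worse than using follow-up FEV1 alone whenever rho is below 0.5.** The general condition is rho < k/2, so 0.5 applies only with equal SDs.
- **That ACQ and AQLQ(S) need the same change.** Sections 5.5.4 and 5.5.8 name no between-arm test for their mean changes, so there is no method there to replace.

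**Conclusion.** The point holds as a modest improvement to an exploratory secondary analysis. In large samples ANCOVA on baseline FEV1 is never less precise than the named t-test on change, and it handles chance baseline imbalance better. That conclusion needs no assumption about FEV1.

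The size does. With equal SDs the variance penalty runs from 5% at a correlation of 0.9 to 54% at 0.3. In the unequal-SD cases shown it ranges from nil (k = 0.8, rho 0.8) to 75% (k = 1.25, rho 0.5). A low correlation is plausible for a baseline taken soon after an attack, but the protocol gives no figure for it or for the SD ratio, so a large loss should not be asserted. The primary Fisher's exact test, its stated 80% power and the sample size are untouched.

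**What to change.** In Section 5.5.5 and the matching Study Abstract text, replace the two-sample t-test. Where FEV1 is compared between arms, use ANCOVA of post-dose FEV1 at each visit, or one repeated-measures model over Days 7, 42 and 84, with Day 0 FEV1 and eosinophil stratum (above 450 against 450 or fewer per mm3) as covariates. Report the adjusted difference between combined MEDI-563 and placebo with its 95% CI. State that the pre-dose Day 0 spirometry value is the baseline. The analysis can remain exploratory.

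The cost is a change of wording in the protocol and, where it covers this analysis, the SAP. Every variable is already scheduled, so no visit, measurement or subject is added. The covariates use up a few degrees of freedom, which matters little with 108 subjects.

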### **5.5.6 Effect of MEDI-563 on Use of Concomitant Controller or Rescue Medications**

The analysis of the effect of MEDI-563 on the need to use concomitant controller or rescue medications through Study Day 84 will be primarily descriptive.

### **5.5.7 Effect of MEDI-563 on Physician Global Assessment**

The PGA will be summarized categorically.

### **5.5.8 Effect of MEDI-563 on Health-related Quality of Life**

Health-related quality of life will be evaluated using the AQLQ(S). The overall score and the 4 domain scores (symptoms, activity limitations, emotional function and environmental stimuli) are the means of the responses to the questions in each of the domains. The analyses will be primarily descriptive. The mean, mean change from baseline, and responder frequency tables will be provided. Individual subjects with score changes of -0.5 or less will be considered responders. A change of -0.5 is considered to be a minimally important difference on the AQLQ(S).

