### **3.6.11.2 Asthma Quality of Life Questionnaire (Standardized Version)**

The AQLQ(S) (see sample in [Appendix 5](#)), will be completed at visits specified in the study schedule. The AQLQ(S) is a 32-item questionnaire that measures the functional impairments experienced by adults 17 years and older ([Juniper et al, May 1999](#)). It has 4 domains (symptoms, activity limitations, emotional function, and environmental stimuli). Subjects are asked to recall their experiences during the previous 2 weeks and to score each of the 32 questions on a 7-point scale from 7 = no impairment to 1 = severe impairment. The overall score is calculated as the mean response to all questions. The 4 domain scores (symptoms, activity limitations, emotional function and environmental stimuli) are the means of the responses to the questions in each of the domains. Individual improvement for both the overall and individual domain scores of 0.5 have been identified as the minimally important difference, with changes >1.5 to be large meaningful differences ([Juniper et al, 1994](#)).

Although not required by protocol, it is preferable if the AQLQ(S) is completed after the ACQ and prior to other assessments.

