**HOW LIMITED HAVE YOU BEEN DURING THE LAST 2 WEEKS IN THESE ACTIVITIES AS A RESULT OF YOUR ASTHMA?**

	Totally Limited	Extremely Limited	Very Limited	Moderate Limitation	Some Limitation	A Little Limitation	Not at all Limited
1. STRENUOUS ACTIVITIES (such as hurrying, exercising, running up stairs, sports)	1	2	3	4	5	6	7
2. MODERATE ACTIVITIES (such as walking, housework, gardening, shopping, climbing stairs)	1	2	3	4	5	6	7
3. SOCIAL ACTIVITIES (as talking, playing with pets/children, visiting friends/relatives)	1	2	3	4	5	6	7
4. WORK-RELATED ACTIVITIES (tasks you have to do at work*) *If you are not employed or self-employed, these should be tasks you have to do most days.	1	2	3	4	5	6	7
5. SLEEPING	1	2	3	4	5	6	7

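### The AQLQ(S) responder rule has the wrong sign: subjects who worsen by 0.5 or more count as responders, and those who improve do not

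*Protocol*

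**What the plan says.** Section 5.5.8 (health-related quality of life) commits to these AQLQ(S) outputs: "The mean, mean change from baseline, and responder frequency tables will be provided". It then fixes the responder threshold, "Individual subjects with score changes of -0.5 or less will be considered responders", and repeats the negative sign in the next sentence: "A change of -0.5 is considered to be a minimally important difference on the AQLQ(S".

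Section 3.6.11.2 describes the instrument. Subjects are asked "to score each of the 32 questions on a 7-point scale from 7 = no impairment to 1 = severe impairment". On aggregation it says: "The overall score is calculated as the mean response to all questions". Domain scores are likewise means of their items, so every AQLQ(S) score keeps the item direction. On the threshold it says: "Individual improvement for both the overall and individual domain scores of 0.5 have been identified as the minimally important difference".

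The questionnaire in Appendix 5 agrees. For the first activity items the response columns, numbered 1 to 7 from left to right, read "Totally Limited Extremely Limited Very Limited Moderate Limitation Some Limitation A Little Limitation Not at all Limited".

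Section 5.5.4 gives the ACQ the same threshold of -0.5. The ACQ is scored from 0 for no impairment to 6 for maximum impairment.

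**The concern.** The two questionnaires run in opposite directions but carry the same negative threshold. On the ACQ a fall is improvement, so -0.5 or less identifies subjects who got better. On the AQLQ(S) a fall is deterioration, so the same rule identifies subjects who got worse. The near-identical wording suggests that the ACQ text was reused, although the protocol does not say so.

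Quality of life measured by the AQLQ(S) is secondary objective 8, and the responder table is one of its planned outputs. If MEDI-563 improves quality of life, a table programmed exactly to Section 5.5.8 would tend to show fewer responders on active treatment than on placebo. Section 5.6 also lists health-related quality of life among the limited endpoints included in the interim analyses, so an inverted table could be produced before the end of the study.

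**Working it through.** **Inputs from the protocol**

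- AQLQ(S): 1 = severe impairment, 7 = no impairment; scores are item means; the minimally important difference is an improvement of 0.5 (Section 3.6.11.2, with matching anchors in Appendix 5).
- AQLQ(S) responder rule: change of -0.5 or less (Section 5.5.8).
- ACQ: 0 = no impairment, 6 = maximum impairment; responder rule: change of -0.5 or less (Section 5.5.4).

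**Step 1. Direction check.** Take change = post-baseline score minus baseline score.

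| Instrument | Baseline to post | Change | Subject | Responder as written | Responder with AQLQ(S) rule of +0.5 or more |
|---|---|---|---|---|---|
| AQLQ(S) | 3 to 5 | +2 | improved | no | yes |
| AQLQ(S) | 5 to 3 | -2 | worsened | yes | no |
| AQLQ(S) | 4.0 to 4.5 | +0.5 | improved | no | yes |
| AQLQ(S) | 4.5 to 4.0 | -0.5 | worsened | yes | no |
| ACQ | 3 to 1 | -2 | improved | yes | not applicable |
| ACQ | 1 to 3 | +2 | worsened | no | not applicable |

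The written rule classifies the ACQ correctly and the AQLQ(S) the wrong way round.

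**Step 2. Does another sign convention rescue it?** Take change = baseline minus post-baseline. AQLQ(S) 3 to 5 then gives -2 and counts as a responder, which is right. But ACQ 3 to 1 gives +2 (not a responder) and ACQ 1 to 3 gives -2 (responder), both wrong. No common convention makes both -0.5 rules mean improvement.

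**Step 3. Illustrative size.** The protocol gives no mean or SD for AQLQ(S) change, so both are assumed. With change taken as normal, mean m and SD s:

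- share labelled responders as written = Φ((-0.5 - m)/s)
- share under the corrected rule = 1 - Φ((0.5 - m)/s)

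| s | m | As written | Corrected |
|---|---|---|---|
| 1.0 | 0.5 | 15.9% | 50.0% |
| 1.0 | 1.0 | 6.7% | 69.1% |
| 1.0 | 1.5 | 2.3% | 84.1% |
| 1.3 | 0.5 | 22.1% | 50.0% |
| 1.3 | 1.0 | 12.4% | 65.0% |
| 1.3 | 1.5 | 6.2% | 77.9% |

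Three two-arm comparisons, active versus placebo:

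- s = 1.0, m = 1.0 versus 0.5: corrected 69.1% versus 50.0%; as written 6.7% versus 15.9%.
- s = 1.3, m = 1.0 versus 0.5: corrected 65.0% versus 50.0%; as written 12.4% versus 22.1%.
- s = 1.2, m = 1.2 versus 0.9: corrected 1 - Φ(-0.583) = 72% versus 1 - Φ(-0.333) = 63%; as written Φ(-1.417) = 8% versus Φ(-1.167) = 12%.

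In each case the apparent direction of the treatment effect reverses. With m = 0 the two rules give equal shares (30.9% at s = 1.0, 35.0% at s = 1.3), so the total could look plausible while the wrong subjects are being counted.

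**The case against.** The strongest objection concerns impact. Section 5.5.8 calls the AQLQ(S) analyses primarily descriptive and also provides the mean and mean change from baseline, which the responder rule does not touch. The protocol specifies no hypothesis test for the AQLQ(S). The mislabelled table would probably conflict visibly with the mean-change table beside it, and a programmer might notice. At the interims, Section 5.6 leaves the detail to the SAP and does not say that the responder table will be shown. The re-estimation and termination rules in Section 5.2.2 use exacerbation proportions only. The illustrative percentages rest on assumed inputs.

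All of this stands, and it confines the damage to the responder table. It does not defend the rule. The minus sign appears in two sentences of current body text, so an extraction error is unlikely. Nor is this a detail left to the SAP: the protocol fixes the threshold and its sign. A SAP that follows the protocol inherits the error, and one that corrects it silently departs from the protocol. A correction made after unblinded interim results could look post hoc.

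**Conclusion.** The concern holds. Section 5.5.8 contradicts Section 3.6.11.2 and Appendix 5, and followed literally it reports subjects whose quality of life worsened by 0.5 or more as responders. The reversal is complete and rests only on the scoring direction the protocol itself gives. Its numerical size depends on the assumed distribution of change: for mean improvements of 0.5 to 1.5 and SDs of 1.0 to 1.3, the written rule labels about 2% to 22% of subjects as responders, against about 50% to 84% under the correct rule.

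The consequence is limited to the AQLQ(S) responder table. The AQLQ(S) mean summaries, the primary endpoint, the planned 108 evaluable subjects, power and alpha are unaffected. The point still needs correcting, because the table would report the opposite of its label.

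**What to change.** In Section 5.5.8, define AQLQ(S) responders as subjects with a score change of +0.5 or more, and give the minimally important difference as +0.5. State that this applies to the overall and the domain scores. Section 5.5.8 does not currently say which score the rule uses, and Section 3.6.11.2 supports the 0.5 threshold for both. It would also help to state that change means post-baseline minus baseline, since the protocol leaves that implicit.

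Leave the ACQ rule in Section 5.5.4 and in the Study Abstract as it is. The AQLQ(S) bullet in the abstract has no responder rule and needs no edit.

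The cost is a correction of two sentences, carried into the SAP and the table programs. There is no effect on data collection or sample size. It should be made before any unblinded AQLQ(S) results are produced.
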